4.1 Inclusion Criteria

Patients who meet all of the following criteria will be eligible to participate:

- 1) Aged between 18-75, male or female;
- 2) With confirmed PA diagnosis (screening positive and at least one confirmatory test is positive);

NOTE: Screening positive is defined as plasma aldosterone-to-renin ratio $(ARR) \ge 20(pg/ml)/(\mu IU/ml)$ or $ARR \ge 300(pg/ml)/(ng/ml/hr)$. Plasma aldosterone concentration (PAC) post captopril challenge test (CCT) ≥ 110 pg/ml or PAC post seated saline infusion test (SSIT) ≥ 80 pg/ml is considered positive. $[ARR \ge 10(pg/ml)/(\mu IU/ml)]$ or $ARR \ge 150(pg/ml)/(ng/ml/hr)$ can be considered positive if the patients with hypokalemia (serum potassium < 3.5mmol/L) or adrenal nodules (diameter > 1cm)].

- 3) Not taking any antihypertensive drugs or on a stable regimen of antihypertensive agents other than MRA for more than four weeks before screening;
- 4) With a mean seated office SBP \geq 140 or DBP \geq 90 mmHg;
- 5) Able and willing to give informed consent for participation in the clinical study.

4.2 Exclusion Criteria

- 1) Planning to have subtyping examinations of PA (eg. adrenal vein sampling, PET-CT) within 3 months;
- 2) Planning to have adrenal surgery or other surgery within 3 months
- 3) With a mean seated office SBP \geq 180mmHg or DBP \geq 110mmHg before randomization;

Note: Mean seated BP is defined as the average of 3 seated BP measurements at any single clinical site visit. If the patient did not take their regularly scheduled antihypertensive medications prior to the visit, 1 BP re-test is allowed within 2 days after taking the medications.

- 4) Night shift worker;
- 5) Has a body mass index (BMI) $\geq 30 \text{ kg/m}^2$ at screening;
- 6) Has uncontrolled diabetes with fasting blood glucose (FBG) ≥13.3mmol/L at screening;
- 7) Has uncontrolled chronic diseases;
- 8) Has other known secondary hypertension (eg, renal artery stenosis, Cushing's syndrome, pheochromocytoma, or aortic coarctation);

- 9) Has known and documented heart failure (New York Heart Association [NYHA] class III or IV), liver transaminase levels are more than twice the upper limit of normal;
- 10) Has had CABG other major cardiac surgery (eg, valve replacement), peripheral arterial bypass surgery, or PCI within 6 months before screening;
- 11) Has had a stroke, transient ischemic attack, hypertensive encephalopathy, acute coronary syndrome, or hospitalization for heart failure within 6 months before screening;
- 12) Has poor compliance that can not fully participate in the study;
- 13) Has hyperkalemia with serum potassium > 5.0mmol/L without potassium supplementation;
- 14) Has a history of uncontrolled malignant tumor;
- 15) The office blood pressure measurements difference of more than 20mmHg in both arms
- 16) Unwilling or unable to stop taking sex hormones, glucocorticoids, non-steroidal anti-inflammatory drugs, cyclosporine, tacrolimus, or antidepressants;
- 17) Is pregnant, breastfeeding, or planning to become pregnant during the study;
- 18) Complicated with severe mental illness;
- 19) Has had prior organ transplant;
- 20) Has a history of allergy to Finerenone or spironolactone;
- 21) Has typical consumption of \geq 15 alcoholic drinks weekly;

Note: 1 drink of alcohol is equivalent to 360ml beer, 45ml spirits, or 150ml wine

- 22) Has participated in another clinical study involving any investigational drug within 30 days prior to screening;
- 23) Female of childbearing potential refusing to use non-hormonal methods of contraception during the study period;
- 24) Refuse to get rid of grapefruit or grapefruit juice while receiving finerenone treatment;
- 25) Other situations that the investigator assesses the subject as unable to complete the trial.

4.3 Withdrawal Criteria

Participation of patients in this clinical study will be discontinued for any of the following reasons:

- 1) The patient withdraws consent or requests discontinuation from the study for any reason;
- 2) Hypertensive emergencies¹⁵, i.e., systolic blood pressure ≥180 or diastolic blood

pressure ≥110mmHg, accompanied by target organ damage, should be withdrawn from the study and treated according to medical routine; Patients with the above mentioned poor blood pressure control during treatment, but no discomfort, can wait for blood pressure retest on the second day, if the systolic blood pressure is still ≥180 or diastolic blood pressure ≥110mmHg, then withdraw from the study;

- 3) The patient used prohibited concomitant medications (refer to 5.5) for more than 1 week, and is still using them 2 weeks before the last visit of the study;
- 4) The patient has any SAE, clinically significant AE, severe laboratory abnormality, intercurrent illness, or other medical condition which indicates to the Investigator that continued participation is not in the best interest of the patient;
- 5) The patient fails to comply with protocol requirements or study-related procedures;
- 6) The patient becomes pregnant.

If a patient withdraws prematurely from the study due to the above criteria or any other reason, they will be requested to undergo the Early Termination Procedures and site staff should make every effort to complete the full panel of assessments scheduled for the End of Treatment (Visit 7). The reason for patient withdrawal must be documented in the case report form (CRF). Patients should still attend study visits after Early Termination for safety monitoring.

In the case of patients lost to follow-up, attempts to contact the patient must be made and documented in the patient's medical records. Withdrawn patients will not be replaced.

4.4 Early Termination Procedures

The End of Treatment for patients completing the study is Visit 7. For patients who are withdrawn from the study prior to completion, all Visit 6 procedures will be performed at the Early Termination Visit.

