Patients will complete at least 5 total visits over the treatment period of 12 weeks, including three Clinic Visits and two Telephone Visits. Clinical Visits (Visit 4, 6 and 7) are conducted on Week 4, Week 8 and Week 12 (the last day of the treatment period), and two Telephone Visits (Visit 3 and Visit 5) are conducted on Week 2 and Week 10. Additional Unscheduled Visits may occur at any time during the study period.

If the office blood pressure remains uncontrolled on Week 4 (ie, systolic blood pressure ≥140mmHg or diastolic blood pressure ≥90mmHg], finerenone and spironolactone will be increased to 40mg per day (the maximum dose). Patients will also be monitored for events of special interest associated with the study medication, including

hyperkalemia, hypotension, impotence, gynecomastia and menstrual abnormalities, in these instances, the dose is either maintained or decreased, as determined by the investigator. When the patient's blood pressure is up to target, if the patient's hypokalemia is not controlled (i.e., the potassium is <3.5mmol on the date of follow-up), thedose will also be increased to 40mg per day.

Study drug (finerenone or spironolactone) dispensing may occur at any time starting at Visit 2 and before Visit 7. On Clinical Visit days, patients will self-administer the morning dose of background antihypertensive medications at home and withhold the study drug. At the clinical site, patients will self-administer the morning dose of study drug under the supervision of site staff after completion of pre-dose evaluations and laboratory sampling. Between clinical site visits, patients will continue taking their study drug once daily by mouth at approximately the same time each morning. The primary efficacy endpoint evaluation will take place at the End of Treatment (Visit 7).

Study visits will follow the Schedule of Procedures (Appendix A).

4. Dosage and Route of Administration:

Finerenone tablets and spironolactone tablets will be administered during the Treatment Period. Finerenone and spironolactone doses to be tested in this study are 20mg or 40 mg.

Patients will receive finerenone tablets of either their assigned dose or matching spironolactone tablets during the Treatment Period, starting at Visit 2 and concluding at Visit 7.

5. Statistical Analyses:

The following analysis populations are defined for the different types of data analysis:

• Intention-to-treat (ITT) Population

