4.5 Criteria for Temporary Suspension of Dosing

Dosing of patients in this clinical study will be suspended temporarily for any of the following reasons:

- Any SAE that is deemed related to the study drug;
- Withdrawal of a patient from the study for safety-related reasons;
- •Mild to moderate AEs that is deemed related to the study drug and the patients could not tolerate continued treatment
- Potassium \geq 5.5 mEq/L; the patient should stop study drug dosing and present to the

clinical site immediately for repeat testing.

5 Study Treatments

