6.3 Treatment Period

6.3.1 Baseline and Randomization (Visit 2, Day 0)

The following procedures will be performed at Visit 2:

- Check inclusion and exclusion criteria;
- Randomization to finerenone or spironolactone once daily;
- Record pre-dose office seated BP;
- Dispense the study drug;
- Record concomitant medications;
- Record adverse events;
- First administration of study drug;
- Perform the following routine safety evaluations pre-dose;
- Record weight;
- Record vital signs;
- Perform physical examination (general appearance, skin, heart, lungs, and abdomen);

6.3.2 Telephone Call (Visit 3 and Visit 5, Week 2 and Week 10 respectively)

The following procedures will be performed at Visit 3 and Visit 5:

- Assess and record AEs;
- Record concomitant medications;
- Perform adherence counselling;
- Record home seated BP;
- Provide the following instructions for the next visit.

Patients should take their scheduled morning doses of background antihypertensive medications at home on the morning of their next visit; Patients must bring their background antihypertensive medications to the clinical site for their next visit; and Patients should not exercise, smoke, or consume caffeinated beverages or food for at least 2 hours prior to the next visit.

6.3.3 Visit 4, Week 4.

The dose used in the assigned regimen will be doubled after 4 weeks if, at that time, the patient remains a mean office seated BP of 140 mm Hg or higher (systolic) or 90 mm Hg or higher (diastolic): at week 4, the dose will be doubled from 20 mg once daily to 40 mg once daily (maximum dose) in both finerenone and spironolactone group.

The following procedures will be performed at Visit 4:

- Assess and record AEs:
- Record concomitant medications;
- Record office seated BP;
- Assess treatment adherence based on pill counts;
- Perform the following routine safety evaluations pre-dose;
- · Record weight;

- Record vital signs;
- Perform physical examination (general appearance, skin, heart, lungs, and abdomen);
- Measure standing BP and heart rate
- Collect blood samples for the following:

Serum potassium

Serum creatinine

6.3.4 Visit 5, Week 8.

Same to the Visit 4

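### The early-termination visit is tied to the wrong visit number (4.4 against 4.3), and amlodipine rescue under 5.6 is not exempted from the prohibited-drug withdrawal rule

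*Protocol*

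**What the plan says.** **Early termination.** Protocol 4.3 sends every prematurely withdrawn patient to the Early Termination Procedures and tells site staff to "make every effort to complete the full panel of assessments scheduled for the End of Treatment (Visit 7". Section 4.4 defines that visit. It first names Visit 7 as the End of Treatment, then says "all Visit 6 procedures will be performed at the Early Termination Visit". Section 4.3 also states: "Patients should still attend study visits after Early Termination for safety monitoring".

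**Visit numbering.** The synopsis (3.2 Study Visit) has "Clinical Visits (Visit 4, 6 and 7) are conducted on Week 4, Week 8 and Week 12", so Visit 6 is Week 8. Appendix A puts Visit 5 at Week 8 and Visit 6 at Week 10. Section 6.3.5 is headed Visit 7, Week 12, but introduces its procedure list as the one for Visit 6.

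**Rescue and prohibited drugs.** Section 5.6 allows amlodipine 5 to 10 mg/day if BP stays at or above 160 systolic or 100 diastolic after 2 to 4 weeks at the maximum dose. Section 5.5.1 excludes every antihypertensive other than the screening-period background treatment. Withdrawal criterion 3 in 4.3 applies to a patient who "used prohibited concomitant medications (refer to 5.5) for more than 1 week, and is still using them 2 weeks before the last visit". Neither 5.5.1 nor criterion 3 mentions 5.6.

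**Primary analysis.** Sections 10.1 and 10.2 compare the change in 24-hour SBP to Visit 7 in the mITT population, which is everyone randomized who took at least one dose. Appendix A schedules ABPM at Visits 1 and 7 only.

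**The concern.** The primary endpoint comes from one post-baseline ABPM, with no interim recording behind it. Withdrawn patients stay in the mITT population, so whether their early-termination visit includes an ABPM decides whether they have any post-baseline value. Two sections give sites different instructions for that visit.

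Some routes into that visit are related to response. One is BP itself: "if the systolic blood pressure is still ≥180 or diastolic blood pressure ≥110mmHg, then withdraw from the study". A second opens if criterion 3 is applied as written, because patients are then withdrawn for taking the rescue drug that the protocol offered them for poor BP control.

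A SAP can decide how to analyse such patients. It cannot supply an ABPM that was not recorded, and it does not decide who is withdrawn. Visit content, prohibited drugs and withdrawal rules are fixed in the protocol.

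**Working it through.** **1. What Visit 6 means.**

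| Source | Visit 6 is | ABPM? |
|---|---|---|
| Synopsis 3.2 | Week 8 clinic visit | No: the Week 8 list in 6.3.4 reads "Same to the Visit 4", and the Visit 4 list has no ABPM |
| Appendix A | Week 10 contact | No: home BP is marked, ABPM is not |
| 6.3.5 | Label on the End of Treatment list | Yes |

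Two of the three uses lead to a visit without ABPM. The first row combines two places, since 6.3.4 itself numbers Week 8 as Visit 5. The third row agrees with 4.3 and suggests that 4.4 and 6.3.5 carry a leftover visit number.

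**2. Rescue against criterion 3, nominal timing.** Inputs: dose raised to 40 mg at Week 4 (5.2), rescue after 2 to 4 weeks at that dose (5.6), last visit at Week 12 = day 84 (Appendix A).

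- Rescue starts at Week 4 + 2 = Week 6 (day 42) to Week 4 + 4 = Week 8 (day 56). Week 6 has no scheduled visit, so that start would need an unscheduled one, which the protocol permits.
- Two weeks before the last visit: 84 − 14 = day 70.
- Use by day 70: 70 − 42 = 28 days, or 70 − 56 = 14 days.

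Both exceed one week, and a patient still on amlodipine at day 70 meets criterion 3 as written.

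**3. The same with visit windows of ±5 days, start at the Week 8 visit.** Week 8 falls on days 51 to 61 and Week 12 on days 79 to 89.

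- Shortest use: (79 − 14) − 61 = 4 days.
- Longest use: (89 − 14) − 51 = 24 days.
- Of 11 × 11 = 121 day combinations, 1 + 2 + 3 + 4 = 10 give 7 days or fewer, so 111 exceed one week.

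**4. Dose first raised at Week 8** (possible under 5.1). Rescue starts at Week 10 at the earliest, so use by day 70 is 70 − 70 = 0 days. Criterion 3 does not say whether the week of use must be complete by then, so the conflict is unclear.

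**5. Timing of an early-termination ABPM.** Withdrawal under criterion 3 at about Week 10 puts it 12 − 10 = 2 weeks before the endpoint.

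**6. Power is not the issue.** From 10.4: SD = √((12.5² + 9.5²)/2) = 11.10, margin 4, one-sided α 0.025, power 80%, and an assumed true difference of 0. The normal approximation gives 121 per arm and the t-based calculation 122, which is the protocol's 244. Then 122/0.8 = 152.5, rounded up to 153 per arm, or 306. With 20% of ABPMs missing, 153 × 0.8 = 122.4 per arm remain and power is 80.5%. The planned loss is covered in number. The point here is which patients are lost.

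**The case against.** **4.3 still asks for the ABPM.** A reader might infer from 4.4 that withdrawn patients will have no post-baseline ABPM. The documents do not support that. Section 4.3 joins the Early Termination Procedures with best effort for the Visit 7 panel, and that request stands under any numbering. The only procedure list in section 6 introduced as Visit 6 is the end-of-treatment list, so a site looking there finds the ABPM. This objection stands. What remains is that sites reading 4.4 beside Appendix A can reach a different answer.

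**5.6 is a specific permission.** A drug that the protocol offers as rescue is not naturally called prohibited, and 1.2.1 expects add-on antihypertensives during the study. The literal reading is probably unintended. Even so, no text says that 5.6 overrides 5.5.1, and criterion 3 refers to 5.5 without exception.

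**Week 12 ABPM after withdrawal.** A reader might call its absence an error. It is not one: an ABPM at withdrawal is already sought, and how patients are handled after leaving treatment may be set in a SAP that is not at hand. Week 12 values after changed therapy could also dilute the contrast between arms, which is anti-conservative for non-inferiority.

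**Bias.** A reader might infer bias towards or against finerenone. The protocol gives no rate of withdrawals under 4.3 or of rescue, by arm or overall, so neither size nor direction can be stated. Confirmed BP at 180/110 or above may be uncommon, since such patients are excluded at entry and rescue is available from 160/100.

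**Conclusion.** Two wording conflicts stand, at low severity. First, 4.4 contradicts 4.3 on the content of the early-termination visit and, under the synopsis or Appendix A numbering, points to a visit without ABPM. The consequence is possible inconsistency between sites in whether the primary measurement is taken. Second, 5.5.1 and criterion 3 do not exempt 5.6 rescue. Applied literally, they withdraw a patient raised to 40 mg at Week 4 and rescued at Weeks 6 to 8, before the Week 12 endpoint and for a reason tied to BP response.

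The second conclusion rests on a literal reading of criterion 3, on amlodipine still being taken at Week 10, and on the dose increase being at Week 4. It holds at nominal timing and, for a start at the Week 8 visit, in 111 of 121 combinations within the visit windows.

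**What to change.** 1. In 4.4 and in the opening line of the 6.3.5 list, change Visit 6 to Visit 7, so that the early-termination visit includes the 24-hour ABPM.
2. Exempt amlodipine given under 5.6 from 5.5.1 and from withdrawal criterion 3, so that rescued patients stay in the study and have the Week 12 ABPM.

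Both are wording corrections and cost almost nothing.

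Optional: withdrawn patients are already asked to keep attending visits, so also record a Week 12 ABPM in those who attend, note any added antihypertensives, and leave the use of that value to the SAP. The cost is one extra recording per such patient.

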4.5 Criteria for Temporary Suspension of Dosing

Dosing of patients in this clinical study will be suspended temporarily for any of the following reasons:

- Any SAE that is deemed related to the study drug;
- Withdrawal of a patient from the study for safety-related reasons;
- •Mild to moderate AEs that is deemed related to the study drug and the patients could not tolerate continued treatment
- Potassium \geq 5.5 mEq/L; the patient should stop study drug dosing and present to the

clinical site immediately for repeat testing.

5 Study Treatments

5.1 Treatment group

Eligible patients will be randomized in a 1:1 ratio to one of the following groups:

- 20mg finerenone; or
- 20mg spironolactone.

We will double the dose of finerenone or spironolactone (up to a maximum dose of 40 mg/d) every 4 weeks if mean office seated BP remains \geq 140/90 mmHg or the hypokalemia is uncontrolled.

5.2 Randomization and Treatment Period

Patients who meet all eligible criteria will be randomized 1:1 into 1 of the 2 treatment groups (finerenone and spironolactone). The dose used in the assigned regimen will be doubled after 4 weeks if, at that time, the patient remains a mean office seated BP of 140 mm Hg or higher (systolic) or 90 mm Hg or higher (diastolic): at week 4, the dose will be doubled from 20 mg once daily to 40 mg once daily (maximum dose) in both finerenone and spironolactone group. The dose will not be increased if the patient has severe TAEs. In these instances, the dose is either maintained or decreased, as determined by the investigator.

5.3 Drug Supplies

After eligible patients randomized into treatment groups, an investigator will dispense the corresponding medication based on the group assignment of the patients.

5.4 Treatment Adherence

At Visits 2 to 7, treatment adherence will be calculated by site staff using pill counts. During the Treatment Period, site staff will collect information from the patient regarding any delays in taking the study drug and missed study drug doses and record them in source files and CRF.

For all protocol-specified doses when the patient is not at the clinical site, patients will self-administer study drug at home and continue taking their background antihypertensive medications. Each patient will be counseled by site staff at every visit on the importance of adhering to their background antihypertensive regimen, study drug, and bringing their medications to each clinical site visit.

5.5 Prior and Concomitant Medications and/or Procedures

5.5.1 Excluded Medications and/or Procedures

- Any antihypertensive medications other than the background treatment in the Screening Period;
- Nonsteroidal Anti-inflammatory Drugs;
- Licorice;
- Strong CYP3A inhibitors (eg. Clarithromycin);
- Strong or moderate CYP3A inducers (eg. Rifampin);
- Glucocorticoid
- Cyclosporine
- Tacrolimus
- Antidepressants
- Estrogenic contraceptives

For CYP3A inhibitors or inducers, see the online reference at

https://www.fda.gov/drugs/drug-interactions-labeling/drug-development-and-drug-interactions-table-substrates-inhibitors-and-inducers.

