5.6 Rescue therapy

If poor blood pressure control persists (SBP≥160mmHg or DPB≥100 mmHg) after adjusting spironolactone or finerenone to the maximum dose for 2 to 4 weeks, amlodipine can be treated remedial (5 to 10mg/day)

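### Rescue amlodipine allowed by section 5.6 is banned by 5.5.1 and can trigger withdrawal under 4.3(3) at Week 10, and 4.3 and 4.4 name different visits for the early-termination assessments

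*Protocol*

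**What the plan says.** **Rescue.** Protocol section 5.6 applies when SBP is at least 160 mmHg or DBP at least 100 mmHg "after adjusting spironolactone or finerenone to the maximum dose for 2 to 4 weeks". In that case "amlodipine can be treated remedial (5 to 10mg/day").

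**Prohibited drugs.** Section 5.5.1 lists as excluded "Any antihypertensive medications other than the background treatment in the Screening Period". Rescue treatment is not exempted there.

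**Withdrawal.** Section 4.3 opens: "Participation of patients in this clinical study will be discontinued for any of the following reasons". Its third reason is that the patient "used prohibited concomitant medications (refer to 5.5) for more than 1 week, and is still using them 2 weeks before the last visit".

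**What happens at withdrawal.** Section 4.3 says that "site staff should make every effort to complete the full panel of assessments scheduled for the End of Treatment (Visit 7"), and also: "Patients should still attend study visits after Early Termination for safety monitoring". Section 4.4 says instead that "all Visit 6 procedures will be performed at the Early Termination Visit".

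**Primary comparison.** Section 10.2 compares the change in 24-hour SBP by ABPM up to Visit 7, which is Week 12.

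**The concern.** Sections 5.5.1 and 5.6 give opposite instructions about the same drug, and section 4.3(3) attaches discontinuation to the prohibited list. Section 4.3(2) already removes patients whose pressure stays at or above 180/110 mmHg. Section 5.6 therefore appears to exist to keep in the trial those between 160/100 mmHg and that limit. Read literally, 4.3(3) removes them again once they have been rescued.

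The reading a centre adopts decides whether a rescued patient stays to the Week 12 ABPM or leaves at about Week 10. A withdrawn patient may still have an ABPM, because section 4.3 asks for the Visit 7 panel, but it would be taken early. Later visits are kept for safety only, and nothing says whether a Week 12 ABPM is then done. Seven centres would each have to choose. An analysis plan can say how post-rescue readings are handled, but it cannot recover a Week 12 reading that was never taken.

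The conflict between 4.3 and 4.4 adds doubt about what is measured at early termination.

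**Working it through.** **Inputs**

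- Dose doubling to the 40 mg maximum: Week 4 (section 5.2). Section 5.1 allows doubling every 4 weeks, so Week 8 is also possible.
- Rescue: 2 to 4 weeks after reaching the maximum dose (section 5.6).
- Last visit: Visit 7, Week 12, day 84 (section 6.3.5).
- Withdrawal rule: more than 7 days of use, and still in use 14 days before the last visit (section 4.3(3)).
- Windows: ±5 days at the Week 8 and Week 12 visits (Appendix A).

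**Nominal dates, doubled at Week 4**

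- Rescue start = Week 4 + 2 to 4 weeks = Week 6 to 8 = day 42 to 56.
- Cut-off = 84 − 14 = day 70 (Week 10).
- Days on amlodipine at the cut-off = 70 − 56 to 70 − 42 = **14 to 28 days**, against a limit of 7. If the drug is continued, both parts of the rule are met across the whole nominal range.

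**With visit windows, rescue started at the Week 8 clinic visit**

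This is the ordinary case, because Appendix A schedules no clinic visit between Weeks 4 and 8.

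- Week 8 visit: day 51 to 61. Week 12 visit: day 79 to 89. Cut-off: day 65 to 75.
- Days at the cut-off = 14 + d12 − d8, where each d is the visit's shift from its nominal day (−5 to +5). Minimum 65 − 61 = **4**; maximum 75 − 51 = **24**.
- Days by the last visit: nominal 28; minimum 79 − 61 = 18; maximum 89 − 51 = 38.
- The patient is on the drug at the cut-off throughout and always exceeds 7 days by the last visit. If the 7 days must be complete at the cut-off, the rule fails only when d8 − d12 is 7 or more, that is, when the two visits move towards each other by at least 7 days in total.

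**Doubled at Week 8**

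Rescue starts at Week 10 to 12, so there are 0 days of use at the nominal cut-off. The point is not claimed for these patients.

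**Meaning of Visit 6, which section 4.4 relies on**

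| Place in the protocol | Visit 6 is | ABPM |
|---|---|---|
| Synopsis, Study Visit | Week 8 clinic visit | Not stated there |
| Appendix A | Week 10; home BP marked, no potassium or renal function | No |
| Section 6.3.5 | The label on the Week 12 procedure list, under a Visit 7 heading | Yes |

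Staff who follow 4.4 with Appendix A would do no ABPM, potassium or renal function test at early termination. Staff who follow 4.4 with 6.3.5, or who follow 4.3, would do all three.

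**The case against.** The strongest reply is structural. Section 5.6 is a specific permission for a named drug, with a dose and a pressure threshold, and it follows a general ban; such a permission is ordinarily read as the exception. Section 1.2.1 also foresees add-on antihypertensives during the study. That is probably what was meant. It stands as an account of intent, but no section writes the exception. The 2-week clause in 4.3(3) can also be read as deliberate, since it tolerates earlier use and acts only when use runs close to the final measurement.

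Other limits stand and narrow the point:

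- The trigger needs amlodipine to be continued to Week 10, and section 5.6 gives no duration.
- A start before Week 8 needs an unscheduled visit, so 14 days is the usual nominal figure and 28 the extreme.
- The synopsis allows dihydropyridines as background. A patient already on amlodipine is outside the literal ban, although a dose increase is not addressed.
- If days are counted to the last visit, a patient doubled at Week 8 and rescued at Week 10 would have 14 days by Week 12. Leaving that group out is therefore the cautious choice.

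On the visit number, the only list introduced as Visit 6 procedures is the Week 12 list with ABPM, so 4.4 probably means the same as 4.3. That makes it a numbering conflict, not a plan to omit the ABPM. It still needs correcting, because Appendix A supports the opposite reading.

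**Conclusion.** The concern holds. As written, a patient without background amlodipine who is doubled at Week 4, rescued at Week 6 to 8 and kept on the drug meets the withdrawal rule at Week 10 for taking treatment that the protocol permits. Nominal exposure at that point is 14 to 28 days against a limit of 7. For rescue at the Week 8 visit it is 4 to 24 days across the windows, and the rule can fail only if the week must be complete at the cut-off and the two visits close up by 7 days or more.

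Separately, 4.3 and 4.4 name different visits for the early-termination assessments.

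The consequence is uncertainty over whether rescued patients reach the Week 12 primary measurement. The protocol gives no rescue rate, so neither the number of patients nor any size or direction of bias can be stated. This should be corrected as an inconsistency in the conduct rules; it does not call the design or the sample size into question.

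**What to change.** Make four short edits to the protocol:

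1. Section 5.5.1, antihypertensive item: add *except rescue amlodipine under 5.6*.
2. Section 4.3(3): add the same exception, so that rescued patients stay through the Week 12 ABPM.
3. Section 4.4: replace the reference to Visit 6 with *Visit 7 procedures, including 24-hour ABPM*, to match 4.3.
4. Section 6.3.5, line under the heading: change Visit 6 to Visit 7.

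The cost is a few words. No new data are needed and the target of 306 patients is unchanged. The small downside is that the main comparison will include ABPM readings taken on amlodipine; how those are analysed is a matter for the SAP.
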